Gait and balance disturbances in MS are already common even in the early stages of the disease. Half of the patients refer some alteration in the quality of their gait within the first month after diagnosis, reaching 90% at 10 years of evolution.⁴ ⁵ Furthermore, gait is the most valuable body function for MS patients, both for those with less than 5 years of evolution and for those with more than 15 years, as walking restriction hardly affects their activity and participation level.⁷

Gait disturbance is caused by multiple factors such as decreased muscle strength, balance, coordination, and proprioception, impaired vision, spasticity, fatigue and even cognitive impairment.⁴

Some impairments arise in the physical and social context of each patient, limiting participation in activities or therapies to improve balance, fatigue, strength and gait characteristics such as fatigue, high risk of falls or high disability.⁷

This would support the development and application of rehabilitation strategies for mitigating the energetic penalties of gait abnormalities during ambulation. Some of these interventions include aerobic, resistance, yoga, and combined exercise training, that have shown significant improvements in walking endurance regardless of outcome measures (6MWT, 2MWT).⁸

New emerging approaches might involve Robot-assisted gait training. In the last 5 years a lot of robotic solutions that offer both strategies of support in daily living and rehabilitative devices have appeared. Some studies have shown that people with multiple sclerosis and severe gait impairment who participated in Robot-assisted gait training (RAGT) achieved significant improvement in lower limb muscle strength and increased their walking speed, although the effect was not long-lasting.⁹

In the last years evidence about robot-based rehabilitation for PwMS has been published, and currently, more than 5 devices have been approved for its use in gait neurorehabilitation. Yeh et al. concluded that Robotic locomotor training limitedly affects motor functions of multiple sclerosis, but improves fatigue and spasticity, it is safe and well-tolerated for PwMS and less demanding for physical therapists.¹⁰ Bowman et al. concluded that Robotic-Assisted Gait therapy (RAGT) improves balance and gait out-

comes in a clinically meaningful way in PwMS, RAGT seems more effective compared to conventional rehabilitation, while it shows similar effects if compared to specific balance and gait training in studies with level 2 evidence.¹¹ RAGT has several advantages in terms of patient motor assistance, intensity of training, safety, and the possibility to combine other therapeutic approaches and should be promoted for PwMS with severe disability in a multimodal rehabilitation context as an opportunity to maximize recovery.¹¹ In this context is needed a further larger-scale, better-designed RCTs with a longer training duration and more studies evaluating the satisfaction, usability and effectivity of RAGT.^{10 12 13 11}

The Atalante exoskeleton is composed of an external, powered, motorized orthosis that is placed over a person's limbs to provide self-ambulation functions without the use of crutches or other technical aids. The main feature of the exoskeleton is that it is fully actuated with 12 actuated degrees of freedom: three at each hip, one at each knee, and two at each ankle.^{14 15}

The molecular bases associated with the functional improvements derived from rehabilitation therapies or physical exercise are not yet well defined. However, both rehabilitation and exercise have been recognized for their immunomodulatory properties. In fact, recent clinical and preclinical findings have established a connection between physical activity and rehabilitative interventions with discernible epigenetic alterations in immune cells. For example, recent preclinical research has demonstrated how moderate-intensity training induces lasting changes in chromatin accessibility in macrophages, resulting in moderation of their inflammatory responses. However, there is still a lack of comprehensive epigenomic studies examining the repercussions of rehabilitation therapies in individuals with multiple sclerosis.

2 Aims

2.1 Primary Aim:

- To compare the effect of RAGT by use of Atalante self-balance exoskeleton with conventional rehabilitation training (cRHB) for improving **Walking speed** measured by the Timed 10-meters walk test (10-MWT), considering a clinically relevant change an improvement of 20% of the velocity (m/s) with respect to the baseline assessment.¹⁶

2.2 Secondary Aims:

- To compare the effect of RAGT by use of the Atalante self-balance exoskeleton with conventional Rehabilitation training (cRHB), for improving **static balance**, **dynamic balance**, mobility, and **self-perception of gait impairment** measured with:
 - **Static Balance** by the Berg Balance Scale (BBS), considering a clinically relevant change for improvement in balance as measured by BBS was +3 points, meaning that PwMS are likely to perceive that as a reproducible and clinically important change in them balance performance.¹⁷
 - **Dynamic balance** by the Timed Up and Go test (TUG)¹⁸
 - **Mobility** measured by modified Rivermead Mobility Index (mRMI)¹⁹

- **Self-perception of gait** impairment by Multiple Sclerosis Walking Scale-12 (MSWS-12)²⁰
- **Instrumented gait analysis** by the G-walk device (assessing gait cycle duration, step length, propulsion index, support phase percentage D/I, oscillation phase percentage D/I, double/unique support phase percentage).
- To compare the effect of RAGT by use of the Atalante self-balance exoskeleton with conventional Rehabilitation training (cRHB) on quality of life, emotional status and fatigue measured at pre and post-intervention with:
 - Multiple Sclerosis Quality of Life-54 (MSQoL 54 Health Survey Spanish version)²¹
 - Hospital Anxiety and Depression Scale (HADs) considering a clinically relevant change of 1.7 points at HADs²²
 - The Modified fatigue scale (MFIS) ^{23 24}
 - The patient' physical effort of each session by means of the scale of perception of the effort R.P.E of Borg at the end of each training^{25 26}.
 - To evaluate the epigenetic blueprint of rehabilitation training by comparing the genome wide chromatin accessibility of peripheral blood mononuclear cells (PBMCs) before and after RAGT or cRHB, by Assay for Transposase-Accessible Chromatin sequencing (ATACseq).
 - To test the hypothesis that genome wide chromatin accessibility compared to clinical measures can be useful for identifying molecular mechanisms underlying rehabilitation therapies.
 - To compare the changes induced by RAGT versus cRHB on the overall chromatin accessibility, and specific genome regions and pathways.
 - Use the biological samples to provide additional functional and mechanistic information about the rehabilitation effects and subject health, disease or state.

3 Materials And methods

3.1 Design:

This trial is a prospective, randomized, rater-blinded study (cRHB (N=30) vs RAGT (N=30)).

For the control group, this protocol includes 24 one-hour sessions of cRHB training during 8 weeks three times per week, under the supervision of a qualified rehab team.

For the intervention group (RAGT) this protocol includes 24 one-hour sessions of RAGT during 8 weeks three times per week, under the supervision of a qualified rehab team.

Additionally, peripheral blood (6ml) will be taken from all subjects at three timepoints: at baseline (T1), after the 8 weeks of rehabilitation treatment (T2) and, if possible, one year after T4. Biological samples will then be given a unique identifier and transferred to researchers for analysis.

Informed consent will be obtained from patients prior to inclusion in the study, which will be carried out in accordance with the Declaration of Helsinki.

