	Walking in earlygait mode for 5 min directed by the patient	Squat exercise 1 series x 10 rep.	Squat exercise 1 series x 10 rep.	Squat exercise 1 series x 10 rep.	Squat exercise 1 series x 10 rep.
	Squat exercise 1 series x 10 rep.	Trunk control exercises with ball for 5 min.	Trunk control exercises with ball for 5 min.	Trunk control exercises with ball for 5 min	Trunk control exercises with ball for 5 min.
	Trunk control exercises with ball for 5 min.	Squat exercise 1 series x 10 rep.	Squat exercise 1 series x 10 rep.	Squat exercise 1 series x 10 rep.	Squat exercise 1 series x 10 rep.
	Squat exercise 1 series x 10 rep.	Trunk control exercises with balloon 5min.	Trunk control exercises with balloon 5min.	Trunk control exercises with balloon for 5 min	Trunk control exercises with balloon for 5 min
	Trunk control exercises with balloon for 5 min.	Squat exercise 1 series x 5 rep.	Squat exercise 1 series x 10 rep.	Squat exercise 1 series x 10 rep.	Squat exercise 1 series x 10 rep.
	Walking in earlygait mode for 5 min + dual task.	Walking with earlygait 5min dual task.	Trunk control exercises with racket/basketbal l for 5 min.	Trunk control exercises with racket/basketbal l for 5 min.	Trunk control exercises with racket/basketbal l for 5 min
Activities	Walking in earlygait mode for 10 min (We adjust assistance levels)	Walking in earlygait mode for 5 min (We adjust assistance levels)	Walking in realgait mode for 5 min, introducing dual task.	Walking in realgait mode for 10 min directed by the patient (We adjust assistance levels).	Walking in realgait mode for 10 min directed by the patient (We adjust assistance levels).

	Introduce use of the controller by the patient in realgait 5min.	Walking in realgait mode for 10 min directed by the patient (We adjust assistance levels).	Walking in realgait mode for 5 min, training dual task.	Walking in realgait mode for 5 min, training dual task.
--	--	--	---	---

4 Statistical considerations

The sample size calculation was based on the observed success rate (70%) in a previous evaluation of safety and performance of the self-balancing walking system Atalante in patients with spinal cord injury (i.e., 10 mWT with continuous walking mode)¹⁵

A sample size of 15 patients had been deemed necessary to demonstrate the performance with an alpha risk of 5% and a statistical power of 80% (Two-sided test).

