Descriptive statistics (i.e., mean, standard deviation) will be calculated for quantitative data (demographics and clinical characteristics and outcome measures). Frequencies will be calculated for qualitative variables. For the proportions, binomial proportion confidences will be calculated using the Wilson formulae. Proportions will be compared using the Newcombe formulae

The Wilcoxon bilateral matched-pairs test will be used to compare repeated measurement on a single sample (mean, standard deviation).

Study data were collected and managed using REDCap electronic data capture tools hosted at the Mayo Clinic. REDCap (Research Electronic Data Capture) is a secure, web-based application designed to data capture for research studies, providing: 1) an intuitive interface for validated data entry; 2) audit trails for tracking data manipulation and export procedures; 3) automated export procedures for seamless data downloads to common statistical packages; and 4) procedures for importing data from external sources (Harris et al., 2009).

5 References

6. Larocca NG. Impact of Walking Impairment in Multiple Sclerosis Perspectives of Patients and Care Partners Conclusions: Difficulty walking is a common impairment in people with MS, with adverse effects on the QOL of people with MS and care partners of a person with MS. *Patient.* 2011;4(3):189-201.

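### Section 4 offers no between-arm analysis of walking speed on its continuous scale, so as written the primary comparison can be tested only through the 20% threshold, which would cost power

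*Combined protocol and SAP*

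**What the plan says.** - **Outcome.** Section 2.1 sets the primary comparison on walking speed, "measured by the Timed 10-meters walk test (10-MWT"), in m/s, and adds: "considering a clinically relevant change an improvement of 20% of the velocity (m/s) with respect to the baseline assessment". It does not say that the endpoint is the proportion of patients reaching 20%.
- **Parallel wording.** Section 2.2 treats the Berg scale the same way, "considering a clinically relevant change for improvement in balance as measured by BBS was +3 points", and gives 1.7 points for HADS.
- **Design.** Section 3.1: "This trial is a prospective, randomized, rater-blinded study (cRHB (N=30) vs RAGT (N=30" each).
- **Sample size.** Section 4: "The sample size calculation was based on the observed success rate (70"%), taken from a study of the device in spinal cord injury. Then: "A sample size of 15 patients had been deemed necessary to demonstrate the performance". The error rates given are a two-sided alpha of 5% and 80% power.
- **Analysis.** Section 4 summarises quantitative outcomes by mean and SD. It uses a Wilcoxon matched-pairs test for repeated measurements within a single sample. For proportions it gives Wilson intervals and states: "Proportions will be compared using the Newcombe formulae". It does not tie any of these to the primary aim. The only other between-group model, edgeR in section 3.4, is for chromatin data.

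**The concern.** The 10-MWT gives a speed for each patient. If the arms can be contrasted only as proportions, that speed must first be reduced to whether the gain reached 20%. A patient at +19% then counts the same as one at -30%, and +21% the same as +90%. A small timing error near the threshold can flip a patient's result.

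With 30 patients per arm there is little information to spare. A real difference between the arms becomes more likely to be missed, although the measurements needed for a sharper comparison are already scheduled at T1 and T2.

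**Working it through.** **1. Inputs.** From the documents: 30 per arm, two-sided 5%, target power 80%, a 70% success rate and a 20% threshold. Not given: the control-arm responder rate, the SD of speed or of its change, the shape of its distribution, and the expected difference in speed. These are assumed below and varied.

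**2. The plan's own figure of 15.** It cannot be reproduced, because no comparator or null rate is stated. It can be matched only by supplying one.
- Two arms, 70% vs an assumed 20%: [1.960 × √(2 × 0.45 × 0.55) + 0.842 × √(0.21 + 0.16)]² / 0.50² = 14.3, so 15 per arm.
- One sample, 70% vs an assumed 35%: [1.960 × √(0.35 × 0.65) + 0.842 × √0.21]² / 0.35² = 14.2, so 15 in total.

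The text does not say which was meant, or how 15 leads to 30 per arm. What it shows is that the size was built on a rate and not on a difference in speed.

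**3. What section 4 allows.** Means and SDs describe. The matched-pairs test works within one sample. Only the Newcombe comparison contrasts two arms on a clinical outcome, and it needs a yes/no variable. The 20% threshold is the only cut the plan offers for speed.

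**4. Information kept after a cut (normal data, small effects).** Relative efficiency = φ(z_p)² / [p(1 − p)], where p is the pooled responder rate.

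| Pooled rate | Efficiency | 60 patients are worth |
|---|---|---|
| 50% | 0.637 (= 2/π) | 38.2 |
| 40% or 60% | 0.622 | 37.3 |
| 30% or 70% | 0.576 | 34.5 |
| 20% or 80% | 0.490 | 29.4 |
| 10% or 90% | 0.342 | 20.5 |

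So 38 is the ceiling under normality.

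**5. Check at a realistic effect (70% vs an assumed 40%, 80% power).**
- Cut: [1.960 × √(2 × 0.55 × 0.45) + 0.842 × √(0.21 + 0.24)]² / 0.30² = 42.0, so 42 per arm.
- Uncut: d = z(0.70) − z(0.40) = 0.524 + 0.253 = 0.778; 2 × (1.960 + 0.842)² / 0.778² = 25.9, so 26 per arm.
- 60 × 26/42 = 37.1. Control rates from 30% to 60% give 36.1 to 37.5.

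**6. Power with 30 per arm (simulated; RAGT 70%, control rate assumed).** The cut is judged by whether the Newcombe 95% interval excludes zero. The other two tests use the uncut change.

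| Change distribution | Control rate | Cut | Rank-sum | t-test |
|---|---|---|---|---|
| Normal | 30% | 89% | 97% | 98% |
| Normal | 40% | 67% | 82% | 84% |
| Normal | 50% | 35% | 49% | 52% |
| t, 5 df | 40% | 67% | 76% | 70% |
| t, 5 df | 50% | 35% | 44% | 39% |

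Repeat runs agree to within about one percentage point. The SD drops out because the shift between arms is set from the two responder rates; that is by construction and is not evidence of robustness. Any further gain from adjusting for baseline is not counted.

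**The case against.** **The cut is not stated.** A reader might infer that the plan defines its primary endpoint as the proportion gaining 20%. The documents do not say so. The 20% is called a clinically relevant change, in wording that section 2.2 also uses for the Berg scale and HADS, where it reads as an aid to interpretation. Section 4 also summarises quantitative outcomes uncut. This objection stands, and the point is therefore conditional. It does not rescue the plan: if 20% is only a benchmark, section 4 contains no between-arm test of the primary outcome at all.

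**The 70% is not a 20%-gain rate.** It is a success rate on the 10-metre walk with the device in spinal cord injury. Nothing shows that it counts patients who improved by 20% over baseline, so it should not be read as the expected responder rate here. It is used above only as the one rate the plan supplies.

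**The size depends on the distribution.** A reader might take 38 of 60 as a fixed figure. It needs normal data and a pooled rate near 50%. With t (5 df) data, a median cut is about 77% as efficient as the rank-sum test, which is about 46 of 60. Against a t-test the loss nearly vanishes (67% vs 70%). This also stands.

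**A responder comparison is legitimate.** Testing a cited threshold answers a real clinical question, and lower power is its price. That is fair if the choice is deliberate and the trial is sized for it. Section 4 shows neither.

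**A continuous analysis has its own gap.** Section 3.2.1 admits EDSS 6.0 to 7.0 and does not require the ability to walk 10 m. Log velocity is undefined at zero speed, and percentage change is undefined at zero baseline. This is correct and has to be part of the fix. The 20% criterion has the same difficulty, since 20% of zero is zero.

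**Conclusion.** The point holds in conditional form. Section 4 provides no between-arm analysis of walking speed as a continuous variable, and the only route it offers to a test between the arms is a comparison of proportions at the 20% threshold.

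If that cut is the endpoint, at least about 36% of the information is lost under normality (1 − 2/π = 0.363), and more when responders are rare or very common. At assumed rates of 70% vs 40%, the chance of missing the difference is about 33% with the cut and 16 to 18% without it. With heavy tails (t, 5 df) it is 33% against 24% (rank-sum) or 30% (t-test).

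The missing primary analysis is plain from the text. The cut is an inference, and the size of the loss rests on a control rate and a distribution that the documents do not give. The change should be made, ideally before any between-arm data are seen.

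**What to change.** In section 4:

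1. Name the primary between-arm analysis: 10-MWT velocity at T2 on the continuous scale, adjusted for baseline velocity. ANCOVA on velocity or log velocity would serve, or a rank-based version. Report the estimated difference with its 95% CI. Section 2.1 names no time point, so T2 should be stated as the primary one.
2. State in advance how patients who cannot complete the walk, at baseline or at T2, enter the analysis, for example as speed 0 or worst rank in a rank-based analysis. If log velocity is chosen, a separate rule for zero speed is needed.
3. Keep the 20% responder difference, with its Newcombe interval, as the supportive result on clinical relevance, and define a responder for patients with zero baseline speed.

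**Cost.** This is a wording change plus one real decision, on non-completers. It needs no new visits, patients or measurements, because velocity is already collected at T1 and T2. The small downside is that the headline becomes a difference in speed, with the responder rate second.

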3.6 Intervention

The intervention will be delivered through the Neurorehabilitation Cemcat team.

Traditional Gait Rehabilitation training (tRHB):

Participants randomize to receive a tRHB, will be trained 3 times per week, with an intensity of 40 to 60 minutes, and duration over 8-weeks. Progression will occur by increasing the session intensity weekly.

A standardized protocol based on the usual clinical practice of physiotherapy in people with multiple sclerosis will be follow, according to patient characteristics, to design the sessions based on the patient objectives to be achieved, choosing the type of specific exercises to be performed based on the patient's condition and with the possibility of adapting them to their evolution during the twenty-four sessions.

PHYSIOTHERAPY TREATMENT PROTOCOL			
Goal	To re-educate the balance (sitting and standing).	To normalize upper limbs muscle tone	To improve the upper limbs muscular balance (MB)
Intervention	Trunk work on stable surface: anterior-flexion, lateralization and turns to make appear the straightening reactions (5 minutes)	Local cryotherapy application to the most affected muscles using cold-packs (15 minutes)	If BM = 1: isometrical exercises of deltoid, bicep, triceps, carpal extensors and carpal flexors (3 sets of 5 repetitions for each muscular group)
	Trunk work on instable surface (air cushion): anterior flexion, lateralization and turns to make appear the straightening reactions (5 minutes)	Inhibitory postural treatment in flexion, abduction and external rotation of humeral-scapula for the flexor patterns during cryotherapy application	If MB = 2: Weight-bearing and/or active-assisted exercises for deltoids, biceps, triceps, carpal extensors and carpal flexors (3 sets of 5 repetitions for each muscle group)
	Balance work with Bobath ball (5 minutes)	Passive mobilizations and myotendinous stretching of spastic musculature (5 minutes)	If MB= 3 : active-resisted exercises with $\frac{1}{2}$ kg of deltoid, bicep, triceps, carpal extensors and carpal flexors (3 sets of 5 repetitions for each muscular group)
	Balance standing exercises at bars: antero-posterior and lateral load transfer, different support bases, and changing props and surfaces (10 minutes)	Pectoral and brachial biceps kneading and lats stretching (5 minutes)	If MB = 4: active-resisted exercises with 1 kg of deltoid, bicep, triceps, carpal extensors and carpal flexors (3 sets of 5 repetitions for each muscular group)

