	Running treadmill with speed and inclination according to tolerance (2-6 minutes)	Passive verticalization at standing or inclined plain to reduce the flexor musculature hypertonia (10 minutes)	If MB = 5: active-resisted exercises with 2 kg of major glutes, psoas, quadriceps, hamstrings and anterior tibial (3 sets of 5 repetitions for each muscular group)
	Weight-bearing walking (5 minutes).	Active verticalization at the shoulders or parallel bars in order to reduce the hypertonia of the flexor muscle (5-10 minutes)	Step from sitting to standing (3 sets of 5 repetitions)
	Vibratory stimulation in bilateral plantar zone (5 minutes)	Antero-posterior and lateral pelvic tilting exercises to encourage straightening reactions and reduce upper limbs hypertonia. (5-10 minutes)	Go up and down 20 stair's steps
		Pelvic and trunk rotations to decrease trunk extension hypertonia (5 minutes)	Active-resisted cycloergotherapy, resistance according to symmetry (10 minutes)
		Passive cycle ergotherapy adapting speed to tolerance and avoiding spasms during exercises (10 minutes).	

Atalante Gait training (RAGT):

Participants randomize to receive a Atalante gait training, will be trained 3-times per week, with an intensity of 40 to 60 minutes, and duration over 8-weeks. Progression will occur by increasing the session intensity weekly. Training intensity will be monitored and standardized using the Borg Rating of Perceived Exertion scale, and will progress from 'fairly light' to 'somewhat hard'. This prescription is consistent and appropriate for individuals with MS with mobility impairment and low fitness levels. Progression will occur by increasing the intensity of the session increase the number of steps in each session and decrease the level of assistance. Sessions will not exceed 60 minutes. We will record all training parameters.

Using the Atalante System, participants will be secured with the appropriately sized harness and attached to an overhead body-weight support system. Each session will begin with a 3–5-minute warm-up in the continuous passive mode (cadence ~40-45 steps/minute). The participant will then be transitioned into the adaptive training phase for practicing repetitive floor walking for up to 30 minutes. During this phase, the force produced by the robot is modulated to support the effort of the patient in producing a typical walking pattern.

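### Borg exertion is listed as a comparative effect measure, but RAGT intensity is set on the same scale, so a between-arm difference cannot be read as a treatment effect

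*Combined protocol and SAP*

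**What the plan says.** Borg exertion appears in three places in the combined protocol and SAP.

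- **Section 2.2, Secondary Aims.** One aim reads "To compare the effect of RAGT by use of the Atalante self-balance exoskeleton with conventional Rehabilitation training (cRHB) on quality of life, emotional status" and continues with fatigue. Its measures are introduced by "emotional status and fatigue measured at pre and post-intervention with". The list holds the MSQoL-54, the HADS, the MFIS and the patient's "physical effort of each session by means of the scale of perception of the effort R.P.E of Borg", scored when each session ends. Nothing marks the Borg item as a process, safety or tolerability measure.
- **Section 3.6, Intervention, RAGT arm.** "Training intensity will be monitored and standardized using the Borg Rating of Perceived Exertion scale, and will progress from 'fairly light' to 'somewhat hard". The means of progression are to "increase the number of steps in each session and decrease the level of assistance". The session table that follows lowers robot assistance from 100% in the first session to 60% in week 8, adapted to the patient's capacity. All training parameters are to be recorded.
- **Section 3.4, Table 1.** Borg stands under the outcome type Effort, separate from Fatigue (MFIS). It has a single mark, apparently in the column for sessions 1 to 24, and none at baseline or end of training. That column is labelled for robotic sessions.

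For the control arm (called tRHB in Section 3.6), the intensity rule is only "Progression will occur by increasing the session intensity weekly". That sentence also appears for RAGT, but the control text adds no Borg level and no other intensity scale. Section 4 gives no analysis specific to Borg.

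**The concern.** The same score has two roles that do not fit together. As an outcome, it should be free to respond to treatment. As the scale on which intensity is standardised, it is meant to be held near a planned level, and in the RAGT arm that level is planned to rise.

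If Borg is analysed as Section 2.2 lists it, two misreadings are open. A rise over the weeks under RAGT could be reported as greater effort or fatigue, when it would mainly show that the training plan was followed. A difference from cRHB could be reported as an effect of the exoskeleton, when it would largely compare a prescribed intensity with one for which no Borg level was prescribed. Randomisation and rater blinding protect against neither, because the level is set by the protocol and not by chance imbalance or by the rater.

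**Working it through.** No arithmetic applies. The point depends on the role given to one measure and not on alpha, power, effect size or sample size. The check is to set the sections side by side.

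**1. Is Borg a comparative measure?** As written, yes. It is listed in Section 2.2 under an aim to compare the two arms, next to three questionnaires that are plainly outcomes.

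**2. Is Borg also a target in one arm?** Yes. Section 3.6 says that RAGT intensity is monitored and standardised on this scale, and names a start level and a later, higher level.

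**3. Is it a target in the other arm?** No. Intensity in the control arm rises weekly, but the text ties it to no Borg level.

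**4. What would a within-arm rise under RAGT mean?** The plan itself calls for a rise. Observing one is what adherence would produce, whether or not the treatment changes fatigue. If a patient became fitter and the load were raised to keep to the planned exertion, a real benefit would not show in the score at all.

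**5. What would a between-arm difference mean?** At least three explanations would give the same result: the RAGT prescription lies above or below the intensity that cRHB happens to reach; therapists keep to the prescription to differing degrees; or patients find one form of training harder at a similar load. The plan has nothing that separates these, and none of them is an effect on fatigue.

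**6. Is there a pre-intervention value?** No. The aim calls for measurement before and after the intervention, but a score given at the end of a training session does not exist before training starts. Table 1 agrees: it shows no Borg mark at baseline. Section 4 names a matched-pairs Wilcoxon test for repeated measurements on a single sample. If the first and last sessions were used as the pair, the test in the RAGT arm would mainly ask whether the planned progression took place.

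**7. Does it matter whether cRHB sessions are scored?** The session column of Table 1 is labelled for robotic sessions, so collection in the control arm is not clearly planned. The table was read by a program and the column placement is uncertain, so nothing here rests on it. Scoring both arms would make a comparison possible, but would not change what the RAGT score reflects.

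**The case against.** The strongest case on the other side has four parts.

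- **The list layout in Section 2.2 is unreliable.** The chromatin-accessibility aims sit at the same level under the same lead-in and clearly do not belong to it. The Borg line names its own construct and its own timing, so it may be a descriptive item that was misplaced. This is a fair caution about intent. But no other text gives Borg a different status, so a reader following the plan would treat it as comparative.
- **Table 1 already separates effort from fatigue.** This stands, and it means that the MFIS is already the fatigue measure in the schedule. It does not take Borg out of the comparative aim.
- **The scores are not fully dictated by the plan.** Section 3.6 gives no Borg value by week and no rule for changing a session when the score is off target. The load also follows a weekly schedule adapted to capacity. This stands. A reader might infer that Borg under RAGT carries no information beyond the prescription, or that the comparison is wholly circular. The documents do not support that: scores can depart from the plan, and the departures say something about tolerance and adherence.
- **The size cannot be stated in scale points.** This also stands. A reader might turn the two verbal levels into numbers and claim a fixed rise under RAGT. The protocol states neither the version of the scale nor numerical values for the levels, so no such figure can be drawn from it.

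Nor do the documents say that a rise in exertion will be reported as fatigue or efficacy. The concern is that Section 2.2 permits that reading and Section 4 does nothing to prevent it.

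**Conclusion.** The point holds in a limited form. Borg exertion in the RAGT arm will largely reflect the prescribed intensity, with some remaining information on tolerance and adherence. It has no pre-intervention value. A between-arm difference in it cannot be read as a treatment effect on fatigue or effort.

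The size is a matter of interpretation and not of a number. One of several secondary measures is affected; the primary 10-metre walk, the MFIS and the other outcomes are not. The conclusion assumes that therapists follow Section 3.6 as written, and that the Borg line in Section 2.2 belongs to the aim under which it is listed. If the sponsor never meant it as a comparative measure, the correction is the same and is then only one of wording.

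**What to change.** - In Section 2.2, remove Borg exertion from the measures that compare the effect of the arms. Keep the MFIS as the fatigue outcome.
- State in Section 4 that Borg is reported descriptively, by arm and week, as a measure of delivered intensity and adherence, beside the recorded training parameters.
- Reconcile Section 2.2, Table 1 in Section 3.4, and the two arm descriptions in Section 3.6 on what Borg is for, when it is scored, and whether cRHB sessions are scored as well. A report by arm needs the score in both arms; if it is taken only in RAGT sessions, say so and report that arm alone.

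None of this requires a change to how either arm is trained. The cost is a few lines of text, one fewer comparative secondary outcome and, if cRHB sessions are not already scored, one rating at the end of each of those sessions.
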